### C1. UNANTICIPATED PROBLEMS (UP)

Investigators must also report Unanticipated Problems, regardless of severity, associated with the study drug or study procedures within 24 hours. An unanticipated problem is defined as follows: any incident, experience, or outcome that meets all of the following criteria:

- Unexpected, in terms of nature, severity, or frequency, given the research procedures that are described in the protocol-related documents, such as the IRB-approved research protocol and informed consent document; and the characteristics of the subject population being studied;
- Related or possibly related to participation in the research, in this guidance document, possibly related means there is a reasonable possibility that the incident, experience, or outcome may have been caused by the procedures involved in the research;
- Suggests that the research places subjects or others at a greater risk of harm (including physical, psychological, economic, or social harm) than was previously known or

recognized.

## **C2. DETERMINING RELATIONSHIP OF ADVERSE EVENTS TO STUDY DRUG OR PROCEDURES**

Investigators will be asked to grade the strength of the relationship of an adverse event to cisatracurium or study procedures as follows:

- **Definitely Related:** The event follows: a) A reasonable, temporal sequence from a study procedure; and b) Cannot be explained by the known characteristics of the patient's clinical state or other therapies; and c) Evaluation of the patient's clinical state indicates to the investigator that the experience is definitely related to study procedures.
- **Probably or Possibly Related:** The event should be assessed following the same criteria for "Definitely Associated". If in the investigator's opinion at least one or more of the criteria are not present, then "probably" or "possibly" associated should be selected.
- **Probably Not Related:** The event occurred while the patient was on the study but can reasonably be explained by the known characteristics of the patient's clinical state or other therapies.
- **Definitely Not Related:** The event is definitely produced by the patient's clinical state or by other modes of therapy administered to the patient.
- **Uncertain Relationship:** The event does not meet any of the criteria previously outlined.

## **C3. CLINICAL OUTCOMES THAT MAY BE EXEMPT FROM ADVERSE EVENT REPORTING**

[figure not shown]
Study-specific clinical outcomes of ARDS, as outlined in Sections 3.8.1 and 3.8.2 (Primary and Secondary Outcomes) and Section 6.3 (Assessments During the Study) are exempt from adverse event reporting unless the investigator deems the event to be related to the administration of study drug or the conduct of study procedures (or of uncertain relationship). The following are examples of events that will be considered study specific clinical outcomes

- Death not related to the study drug or procedures.
- Cardiovascular events: need for vasoactive drugs or fluids for hypotension or hypotension.
- Respiratory events: decreased PaO2/FiO2, hypoxia, worsening acute respiratory distress syndrome, or respiratory failure.
- Hepatic events: hepatic injury or liver dysfunction that leads to an increase from baseline in the serum level of bilirubin.
- Renal events: renal failure, renal insufficiency, or renal injury that leads to an increase from baseline in serum creatinine.
- Hematologic/coagulation events: coagulopathy, disseminated intravascular coagulation, thrombocytopenia, or thrombocytosis.

Note: Arrhythmias such as heart block, ventricular tachycardia or ventricular fibrillation are not considered study specific clinical outcomes and should be recorded as adverse events if they are serious events, are considered by the investigator to be related to study drug, or lead to discontinuation of the study drug infusion.

#### C4. DECISION TREE FOR DETERMINING IF AN ADVERSE EVENT IS REPORTABLE

Adapted from Ranieri VM, Thompson BT, Barie PS et al. Drotrecogin alfa (activated) in adults with septic shock. N Engl J Med. 2012 May 31;366 (22):2055-64. Epub 2012 May 22. PubMed PMID: 22616830

## D VENTILATOR PROCEDURES

### D.1 VENTILATOR MANAGEMENT

A modified, simplified version of the ARDS Network lung protective lower tidal volume strategy will be used in this trial. This strategy, which was associated with unprecedented low mortality rates in three previous ARDS Network trials (ARMA, ALVEOLI, and FACTT), will ensure that study subjects receive the beneficial effects of lung protection as part of their participation in this trial [7, 30, 31]. For those patients who remain hospitalized and on mechanical ventilation, the ventilator and weaning protocols will be implemented up to day 90 of hospitalization.

We will also use a modified version of the higher PEEP strategy used in several trials (ALVEOLI, LOV, EXPRESS, OSCILLATE). The use of the high PEEP protocol will be required for up to 5 days after randomization. This strategy has been repeatedly shown to improve oxygenation and to be safe.

PETAL Network personnel have substantial experience in the application of both strategies from the completed trials noted above.

1. Controlled modes of ventilation will be required during the period of neuromuscular blockade. Following neuromuscular blockade, any mode of ventilation capable of delivering the prescribed tidal volume (6ml/kg PBW, +/- 2ml/kg) may be used, provided the  $V_T$  target is monitored and adjusted appropriately. During APRV, tidal volume is defined as the sum of the volume that results from the ventilator pressure-release and an estimation of the average spontaneous  $V_T$ .
2. Tidal Volume ( $V_t$ ) Goal: 6 ml / kg PBW

Predicted body weight (PBW) is calculated from age, gender, and height (heel to crown) according to the following equations:

$$\text{Males: PBW (kg)} = 50 + 2.3 [\text{height (inches)} - 60]$$

$$\text{Females: PBW (kg)} = 45.5 + 2.3 [\text{height (inches)} - 60]$$

3. Measure and record inspiratory plateau pressure (Pplat) according to ICU routine (at least every four hours and after changes in  $V_t$  and PEEP recommended).
4. If Pplat > 30 cm H2O, reduce  $V_T$  to 5 ml / kg and then to 4 ml / kg PBW if necessary to decrease Pplat to ≤ 30 cm H2O.
5. If  $V_T$  < 6 ml / kg PBW and Pplat < 25 cm H2O, raise  $V_T$  by 1 ml / kg PBW to a maximum of 6 ml / kg.
6. If "severe dyspnea" (more than 3 double breaths per minute or airway pressure remains at or below PEEP level during inspiration), then raise  $V_T$  to 7 or 8 ml / kg PBW if Pplat remains below 30 cm H2O. If Pplat exceeds 30 cm H2O with  $V_T$  of 7 or 8 ml / kg PBW, then revert to lower  $V_T$  and consider more sedation.
7. If pH < 7.15,  $V_T$  may be raised and Pplat limit suspended (not required).

8. Oxygenation target: 55 mmHg < PaO2 < 80 mm Hg or 88% < SpO2 < 95%. When both PaO2 and SpO2 are available simultaneously, the PaO2 criterion will take precedence.
9. Minimum PEEP = 5 cm H2O
10. Adjust FiO2 or PEEP upward within 5 minutes of consistent measurements below the oxygenation target range
11. Adjust FiO2 or PEEP downward within 30 minutes of consistent measurements above the oxygenation target range.
12. The below high PEEP strategy FiO2/PEEP table, modified from the ALVEOLI trial , should be used in all patients. See Section 5.3.3 for when deviation is permitted.

FiO 2	.30	.40	.40	.40	.40	.40	.40	.40	.40	.50	.50	.50	.60	.70	.80	.80	.90	1.00	1.00
PEEP	5	5	6	8	10	12	14	16	16	18	20	20	20	20	22	22	22	22	24

If a patient's PEEP/FiO2 is not compatible with the PEEP/FiO2 scale immediately after randomization **either PEEP or FiO2 (or both) will be adjusted in steps, at intervals of 5-15 minutes until the PEEP/FiO2 is compatible with the scale.**

**NOTE: A step is equal to 2 cm H2O of PEEP and/or FiO2 of 0.1.**

(Levels of PEEP in these FiO2 / PEEP scales represent levels set on the ventilator, not levels of total-PEEP, auto-PEEP, or intrinsic-PEEP.)

13. No specific rules for respiratory rate, but incremental increase in the RR to maximum set rate of 35 if pH < 7.30.
14. No specific rules about I:E. Recommend that duration of Inspiration be ≤ duration of Expiration.
15. Bicarbonate is allowed (neither encouraged nor discouraged) if pH < 7.30.

Changes in more than one ventilator setting driven by measurements of PaO2, pH, and Pplat may be performed simultaneously, if necessary.

## D.2 WEANING

### Commencement of weaning

Patients will be assessed for the following weaning readiness criteria each day between 0600 and 1000. If a patient procedure, test, or other extenuating circumstance prevents assessment for these criteria between 0600 and 1000, then the assessment and initiation of subsequent weaning procedures may be delayed for up to six hours. Patients can be assessed for weaning readiness criteria twice a day.

1. At least 12 hours since enrollment in the trial.
2. FiO2 ≤ 0.40 and PEEP ≤ 8 cm

3. Values of both PEEP and  $FiO_2 \leq$  values from previous day (comparing Reference Measurement values, section 6.3).
4. Systolic arterial pressure  $\geq 90$  mm Hg without vasopressor support ( $\leq 5$  mcg / kg / min dopamine will not be considered a vasopressor).

### **Spontaneous breathing trial (SBT) procedure and assessment for unassisted breathing**

If criteria 1-4 above are met, first the neuromuscular blocking agent will need to be discontinued if the medication is still being infused. When the neuromuscular blocking agent has worn off and the patient is having spontaneous respirations, then initiate a trial of up to 120 minutes of spontaneous breathing with  $FiO_2 \leq 0.5$  using any of the following approaches:

1. Pressure support  $\leq 5$ cm H2O, PEEP  $\leq 5$ cm H2O
2. CPAP  $\leq 5$  cm H2O
3. T-piece
4. Tracheostomy mask

Monitor for tolerance using the following:

1.  $SpO_2 \geq 90\%$  and / or  $PaO_2 \geq 60$  mmHg
2. Mean spontaneous tidal volume  $\geq 4$  ml / kg PBW (if measured)
3. Respiratory Rate  $\leq 35$  / min
4.  $pH \geq 7.30$  (if measured)
5. No respiratory distress (defined as 2 or more of the following):
  - a. Heart rate  $\geq 120\%$  of the 0600 rate ( $\leq 5$  min at  $> 120\%$  may be tolerated)
  - b. Marked use of accessory muscles
  - c. Abdominal paradox
  - d. Diaphoresis
  - e. Marked subjective dyspnea.

If any of the goals 1-5 are not met, revert to previous ventilator settings or to PS + 10 cm H2O with Positive End-expiratory Pressure and  $FiO_2 =$  previous settings and reassess for weaning the next morning.

The clinical team may decide to change mode of support during spontaneous breathing (PS = 5, CPAP, tracheostomy mask, or T-piece) at any time.

### **Decision to remove ventilatory support**

For intubated patients, if tolerance criteria for spontaneous breathing trial (1-5 above) are met for at least 30 minutes, the clinical team may decide to extubate. However, the spontaneous breathing trial can continue for up to 120 minutes if tolerance remains in question. If any of criteria 1-5 are not met during unassisted breathing (or 120 minutes has passed without clear tolerance), then the ventilator settings that were in use before the attempt to wean will be restored and the patient will be reassessed for weaning (see section D.2) the following day.

### **Definition of unassisted breathing**

- a) Extubated with face mask, nasal prong oxygen, or room air, OR
- b) T-tube breathing, OR
- c) Tracheostomy mask breathing, OR
- d) CPAP  $\leq 5$  without PS or IMV assistance
- e) Use of CPAP or BIPAP solely for sleep apnea management
- f) Use of a high flow oxygen system

### **Completion of ventilator procedures**

Patients will be considered to have completed the study ventilator procedures if any of the following conditions occur:

- a. Death
- b. Hospital discharge
- c. Alive 28 days after enrollment

If a patient requires positive pressure ventilation after a period of unassisted breathing, the study ventilator procedures will resume unless the patient was discharged from the hospital or > 28 days elapsed since enrollment.

### **Removal from the ventilator management protocol**

Patients may be removed from the 6 ml / kg tidal volume ventilation requirement if they develop neurologic conditions where hypercapnia would be contraindicated (e.g., intracranial bleeding, GCS  $\leq 8$ , cerebral edema, mass effect [midline shift on CT scan], papilledema, intracranial pressure monitoring, fixed pupils).

## E CONSERVATIVE FLUID MANAGEMENT APPROACH

A modified conservative fluid protocol will be used based on the findings from FACTT that conservative fluid management increased ventilator free days. This protocol is recommended for all enrolled patients, to be used until UAB or study day 7, whichever occurs first.

1. Discontinue maintenance fluids.
2. Continue medications and nutrition.
3. Manage electrolytes and blood products per usual practice.
4. For shock, use any combination of fluid boluses# and vasopressor(s) to achieve MAP  $\geq$  60 mmHg as fast as possible. Wean vasopressors as quickly as tolerated beginning four hours after blood pressure has stabilized.
5. Withhold diuretic therapy in renal failure§ and until 12 hours after last fluid bolus or vasopressor given.

This protocol is a simplified modification of the conservative protocol used in FACTT. For patients without a CVC, no fluid gain over the first 7 study days is recommended once patients' blood pressure has stabilized. Stable blood pressure is defined as no requirement for either vasopressors or a fluid bolus to support blood pressure for 12 or more hours.

CVP (recommended)	PAOP (optional)	MAP $\geq$ 60 mm Hg AND off vasopressors for $\geq$ 12 hours	
		Average urine output < 0.5 ml/kg/hr	Average urine output $\geq$ 0.5 ml/kg/hr
>8	> 12	Furosemide* Reassess in 1 hour	Furosemide* Reassess in 4 hours
4-8	8-12	Give fluid bolus as fast as possible # Reassess in 1 hour	No intervention Reassess in 4 hours
< 4	< 8		

§ Renal failure is defined as dialysis dependence, oliguria with serum creatinine > 3mg/dl, or oliguria with serum creatinine 0-3 with urinary indices indicative of acute renal failure.

# Recommended fluid bolus= 15 mL / kg crystalloid (round to nearest 250 mL) or 1 Unit packed red cells or 25 grams albumin

\* Recommended Furosemide dosing = begin with 20 mg bolus or 3 mg / hr infusion or last known effective dose. Double each subsequent dose until goal achieved (oliguria reversal or intravascular pressure target) or maximum infusion rate of 24 mg / hr or 160 mg bolus reached. Do not exceed 620 mg / day. Also, if patient has heart failure, consider treatment with dobutamine.

## F DE-IDENTIFIED DATA ELEMENTS FOR SCREENED, NON-ENROLLED SUBJECTS

The following data elements will be collected on screened subjects who met the inclusion criteria but were not enrolled.

- Did frontal CXR show bilateral infiltrates consistent with pulmonary edema?
- Number of quadrants with opacities?
- Is patient intubated?
- PaO2
- SpO2
- FiO2
- Was there evidence of left atrial hypertension?
- Month of the year that patient met screening criteria (1-12).
- Gender
- Ethnicity
- Age (if age >89, 89 will be entered for age)
- Patient location (e.g. MICU, SICU, etc.) and if regularly screened
- Reason(s) patient excluded from study.
- If not excluded, not enrolled, why?
- Lung injury category (e.g. sepsis, pneumonia)
- If sepsis, site of infection

## G NEUROMUSCULAR AND LONG TERM OUTCOMES

### Phone Interviews for Survivors from All PETAL Study Sites

We will perform phone interviews for vital status and the domains noted in Section 6.4. Centralized vs site-level administration of phone surveys will be determined by the PETAL Steering Committee.

Interviews will be performed by basic research staff using detailed scripts appropriate for each survey instrument. Manuals of Operations will be developed for training, reference and quality assurance review.

## H DATA AND SAFETY MONITORING BOARD

The principal role of the DSMB is to assure the safety of patients in the ROSE trial. They will regularly monitor data from this trial, review and assess the performance of its operations, and make recommendations to the NHLBI with respect to:

- Review of adverse events
- Interim results of the study for evidence of efficacy or adverse events
- Possible early termination of the trial because of early attainment of study objectives, safety concerns, or inadequate performance
- Possible modifications in the clinical trial protocol
- Performance of individual centers

Two interim analyses will be conducted at approximately 33% and 67% target enrollment accrual.

The NHLBI PETAL Network DSMB is appointed by the Director, NHLBI and makes recommendations to the NHLBI Director. The DSMB reviews all protocols for safety following review by an independent NHLBI Protocol Review Committee. The DSMB will consist of members with expertise in acute lung injury, emergency medicine, biostatistics, ethics, and clinical trials. An NHLBI staff member not associated with PETAL will serve as Executive Secretary. Appointment of all members is contingent upon the absence of any conflicts of interest. All the members of the DSMB are voting members. The Principal Investigator and the Medical Monitor of the CCC will be responsible for the preparation of all DSMB and adverse event reports and may review unblinded data. The DSMB will develop a charter and review the protocol and sample consent form during its first meeting. Subsequent DSMB meetings will be scheduled in accordance with the DSMB Charter with the assistance of the CCC. When appropriate, conference calls may be held in place of face-to-face meetings. Recommendations to end, modify, or continue the trial will be prepared by the DSMB executive secretary for review by Director, NHLBI. Recommendations for major changes, such as stopping, will be reviewed by the NHLBI Director and communicated immediately. Other recommendations will be reviewed by the NHLBI director and distributed in writing to the CCC, which will distribute to the PETAL steering committee with instructions for reporting to local IRBs when appropriate.

Details of the NHLBI policies regarding DSMBs can be found at the following URL:

[http://www.nhlbi.nih.gov/funding/policies/dsmb\\_inst.htm](http://www.nhlbi.nih.gov/funding/policies/dsmb_inst.htm)

The PETAL Network Steering Committee is comprised of the Principal Investigators and Co-investigators of all the Clinical sites, the CCC, and the NHLBI Project Officer who represents the NHLBI. All sites have two votes and the CCC has one.

# I AUDIT QUESTIONNAIRE

## The Alcohol Use Disorders Identification Test [80]

The Alcohol Consumption Questionnaire is important to administer because there is a common association between alcohol abuse and ARDS[81]. It will be important to have this information for a subgroup analysis. Knowledge of alcohol abuse will also help the primary team better care for the patient and improve patient outcome, as there are alcohol specific disorders in critically ill patients that often are not diagnosed and therefore not treated effectively. This survey will not be completed on subjects less than 18 years of age.

We will use the modified AUDIT questionnaire (first three questions) as this simplified version has good performance characteristics and is less time consuming.

1. How often do you have a drink containing alcohol?
 
(0) Never [Skip to Qs 9-10]            (1) Monthly or less            (2) 2 to 4 times a month            (3) 2 to 3 times a week            (4) 4 or more times a week
 	
6. How often during the last year have you needed a first drink in the morning to get yourself going after a heavy drinking session?
 
(0) Never            (1) Less than monthly            (2) Monthly            (3) Weekly            (4) Daily or almost daily
 

2. How many drinks containing alcohol do you have on a typical day when you are drinking?
 
(0) 1 or 2            (1) 3 or 4            (2) 5 or 6            (3) 7, 8, or 9            (4) 10 or more
 	
7. How often during the last year have you had a feeling of guilt or remorse after drinking?
 
(0) Never            (1) Less than monthly            (2) Monthly            (3) Weekly            (4) Daily or almost daily
 

3. How often do you have six or more drinks on one occasion?
 
(0) Never            (1) Less than monthly            (2) Monthly            (3) Weekly            (4) Daily or almost daily
 
Skip to Questions 9 and 10 if Total Score for Questions 2 and 3 = 0
 	
8. How often during the last year have you been unable to remember what happened the night before because you had been drinking?
 
(0) Never            (1) Less than monthly            (2) Monthly            (3) Weekly            (4) Daily or almost daily
 

4. How often during the last year have you found that you were not able to stop drinking once you had started?
 
(0) Never            (1) Less than monthly            (2) Monthly            (3) Weekly            (4) Daily or almost daily
 	
9. Have you or someone else been injured as a result of your drinking?
 
(0) No            (2) Yes, but not in the last year            (4) Yes, during the last year
 

5. How often during the last year have you failed to do what was normally expected from you because of drinking?
 
(0) Never            (1) Less than monthly            (2) Monthly            (3) Weekly            (4) Daily or almost daily
 	
10. Has a relative or friend or a doctor or another health worker been concerned about your drinking or suggested you cut down?
 
(0) No            (2) Yes, but not in the last year            (4) Yes, during the last year
 

Record total of specific items here 
 
If total is greater than recommended cut-off, consult User's Manual.
	

## J CISATRACURIUM PACKAGE INSERT AND ACURASYS STUDY PUBLICATION

NIMBEX (cisatracurium besylate) is a nondepolarizing skeletal muscle relaxant for intravenous administration. Compared to other neuromuscular blocking agents, it is intermediate in its onset and duration of action. Cisatracurium besylate is one of 10 isomers of atracurium besylate and constitutes approximately 15% of that mixture. Cisatracurium besylate is [1R-[1 $\alpha$ ,2 $\alpha$ (1'R\*,2'R\*)]-2,2'-[1,5-pentanediy]bis[oxy(3-oxo-3,1-propanediy)]]bis[1-[(3,4-dimethoxyphenyl)methyl]-1,2,3,4-tetrahydro-6,7-dimethoxy-2-methylisoquinolinium] dibenzenesulfonate. The molecular formula of the cisatracurium parent bis-cation is C53H72N2O12 and the molecular weight is 929.2. The molecular formula of cisatracurium as the besylate salt is C65H82N2O18S2 and the molecular weight is 1243.50.

The full package insert and the ACURASYS study primary publication, which together will serve as the Investigator Brochure for this trial, can be found here:

Cisatracurium package insert:

<http://dailymed.nlm.nih.gov/dailymed/drugInfo.cfm?setid=3db3b76c-3e5a-456e-46a8-456fde1e6195>

ACURASYS study: <http://www.nejm.org/doi/pdf/10.1056/NEJMoa1005372>

Note: The mean measured body weights in ACURASYS (+/- SD) were 77 (+/-18 kg; range 43 to 126 kg) in the placebo group and 78 (+/-19 kg; range 30 to 185 kg) in the cisatracurium group (reference 2a)

## K SOFA SCORING SYSTEM

Variables	SOFA Score				
	0	1	2	3	4
Coagulation Platelets x 10  /μL	>150	≤150	≤100	≤50	≤20
Liver Bilirubin, mg/dL	<1.2	1.2-1.9	2.0-5.9	6.0-11.9	>11.9
Cardiovascular Hypotension	No hypotension	Mean arterial pressure <70 mmHg	Dop ≤5 or dob (any dose) ‡	Dop >5, epi ≤0.1, or norepi ≤0.1‡	Dop >15, epi >0.1, or norepi >0.1‡
Renal Creatinine, mg/dL or urine output, ml/d	<1.2	1.2-1.9	2.0-3.4	3.5-4.9 or <500	>4.9 or <200

\*Norepi indicates norepinephrine; Dob, dobutamine; Dop, dopamine, Epi, epinephrine.

†Values are with respiratory support.

‡Adrenergic agents administered for at least one hour (doses given are in μg/kg/min)

We define a clinically significant organ failure as a new SOFA score of ≥ 2.

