#### 2. IL-6 levels (plasma)

We will measure interleukin-6 (IL-6) at study entry and at 48 hours. A proposed mechanism of benefit of neuromuscular blockade is decreased ventilator-induced lung injury. Interleukin-6 is a pro-inflammatory cytokine that decreased in patients treated with a lung-protective low tidal volume ventilation strategy compared to control patients.[7] Furthermore, in pilot studies neuromuscular blockade was associated with decreased levels of IL-6.[13] Here, we hypothesize that compared to control subjects, subjects receiving neuromuscular blockade for 48 hours will have lower levels of IL-6, reflecting decreased ventilator-induced lung injury. As in the ARDS Network trials, analysis of covariance (ANCOVA) will be used to examine the impact of treatment with neuromuscular blockade on biomarker levels at 48 hours.

#### 3. Hospital mortality to day 28

#### 4. Ventilator free days to day 28

Ventilator free days to day 28 are defined as the number of days from the time of initiating unassisted breathing to day 28 after randomization, assuming survival for at least two consecutive calendar days after initiating unassisted breathing and continued unassisted breathing to day 28. If a patient returns to assisted breathing and subsequently achieves unassisted breathing to day 28, VFDs will be counted from the end of the last period of assisted breathing to day 28. A period of assisted breathing lasting less than 24 hours and for the purpose of a surgical procedure will not count against the VFD calculation. If a patient was receiving assisted breathing at day 27 or dies prior to day 28, VFDs will be zero. Patients transferred to another hospital or other health care facility will be followed to day 28 to assess this endpoint.

5. Organ failure free days to day 28

Organ failure is defined as present on any date when the most abnormal vital signs or clinically available lab value meets the definition of clinically significant organ failure according to SOFA scores (Appendix K).[21] Patients will be followed for development of organ failures to death, hospital discharge or study day 28, whichever comes first. Each day a patient is alive and free of a given organ failure will be scored as a failure-free day. Any day that a patient is alive and free of all organ failures will represent days alive and free of all organ failure.

6. ICU-free days at day 28

7. Hospital-free days at day 28

8. Physiologic measures to include:

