## B TIME-EVENTS SCHEDULE

Measurement/Event	Day 0	1	2	3	4	5	6	7	14	21	28	90
Demographics, History and Physical	X											
Etiology of ARDS	X											
APACHE III	X											
HCG (females)	X											
Alcohol Use/Smoking History	X											
CXR (number of quadrants)	X											
Study NMB Administration	X	X	X									
Baseline LTO	X											
Non-protocol NMB administration	X	X	X	X	X							
Level of Sedation	X	X	X	X	X	X	X	X				
Sedation Interruption (y/n)	X	X	X	X	X	X	X	X				
Gross motor assessment				X								
ICU Mobility Scale		X	X	X	X	X	X	X	X	X	X	
Ventilator Parameters#†	X	X	X	X	X			X				
Arterial Blood Gases	A	A	A	A	A			A				
K+, HCO 3 , glucose	A	A	A	A	A			A				
Pneumothorax (y/n)*	X										X	
Use of rescue procedures (y/n)*											X	
Fluids (intake/output)	X	X	X	X	X	X	X	X				
Central Venous Pressure	A	A	A	A	A	A	A	A				
On-study meds: sedative, opioid, corticosteroid administration (y/n)	X	X	X	X	X			X				
SOFA Score (modified) B	X	X	X	X	X	X	X	X	X	X	X	
Manual Muscle Testing (with screening)								X	X	X	X	
Paralysis recall assessment**											X	
Plasma Collection	X	X	X									
Urine Collection	X	X	X									
Whole Blood collection for DNA/RNA	X		X									
Vital Status§											X	X

X=Required

A=When available

†= Data gathered at times indicated or until 48 hours UAB, whichever occurs first

\*\*=Collected once during study hospitalization

B=Records clinically available creatinine, platelets, bilirubin, SBP and vasopressor use

~=Data gathered on days 0-28 or until d/c from study hospital

#=Measure during reference period (0600-1000); other values may be obtained closest to 0800 on the specified calendar date

§=Also measure at 6 and 12 months as part of Long Term Outcome.

\*= Assessed for days 1-28 once on day 28 or discharge

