Renal Creatinine, mg/dL or urine output, ml/d	<1.2	1.2-1.9	2.0-3.4	3.5-4.9 or <500	>4.9 or <200

\*Norepi indicates norepinephrine; Dob, dobutamine; Dop, dopamine, Epi, epinephrine.

†Values are with respiratory support.

‡Adrenergic agents administered for at least one hour (doses given are in µg/kg/min)

We define a clinically significant organ failure as a new SOFA score of  $\geq 2$ .

We treat post-ICU SOFA as normal (i.e. defining organ dysfunction as abnormal SOFA in an ICU); post-ICU means getting out and staying out of ICU; patients are still at risk and have SOFA scores in intervals between ICU readmissions.

Carry forward until home date, death date, last known date in ICU+1, or day29, whichever comes first; patient status decides organ failure free if both status information and SOFA data are available.

We carry last observation forward for any missing data except baseline P/F. Carry forward vasopressors yes/no if taking any vasopressors and missing y/n. Carry forward vasopressor doses if taking this drug and missing dose.

If a patient has missing data at baseline, then the patient would have missing SOFA components, but the total will be the sum of available components scores instead of missing.

Notes: LOCF carries forward each sofa variable rather than carrying forward the computed scores.

### ICU-free days at day 28

Patient will be followed until death, study hospital discharge or study 28, whichever comes first. Any day a patient is alive and out of ICU will be scored as an ICU-free day. There is no penalty for readmission.

#### Hospital-free days at day 28

Hospital free days are counted from hospital discharge through day 28. A patient who is discharged from the study hospital on day 28 is assigned one hospital free day. A patient who is discharged from the study hospital after day 28 is assigned zero hospital free days. A patient who dies prior to day 29 is assigned zero hospital free days.

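### Organ-failure-free days: Appendix K and SAP Appendix A3 do not say how to score dialysis or vasopressors outside four named drugs, so some days on organ support count as failure-free

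*Protocol*

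**What the plan says.** **Outcome.** Organ-failure-free days to day 28 is one of twelve secondary outcomes. Protocol Section 3.9.2, item 5, begins "Organ failure is defined as present on any date when the most abnormal vital signs or clinically available lab value meets" and refers to the SOFA definition in Appendix K. The worst value of each date therefore counts. SAP Appendix A3 reprints the table, and SAP Appendix A1 assigns a t-test.

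**Threshold.** Appendix K: "We define a clinically significant organ failure as a new SOFA score of ≥ 2".

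**Kidney.** The row is headed "Creatinine, mg/dL or urine output, ml/d". Creatinine of 2.0 mg/dL or more scores at least 2. Urine output below 500 ml/d scores 3, and below 200 ml/d scores 4.

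**Circulation.** "Mean arterial pressure <70 mmHg" scores 1. Scores 2 to 4 need one of the drugs named in the footnote: "Norepi indicates norepinephrine; Dob, dobutamine; Dop, dopamine, Epi, epinephrine". They must have been given for at least one hour.

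**Data recorded.** The modified-SOFA footnote in Appendix B reads "Records clinically available creatinine, platelets, bilirubin, SBP and vasopressor use". Neither dialysis nor urine output is in that list. Fluid intake and output is scheduled on days 0 to 7. SOFA is marked on days 0 to 7, 14, 21 and 28.

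**SAP handling.** SAP Appendix A3 carries each SOFA variable forward when missing. For vasopressors it says "Carry forward vasopressors yes/no if taking any vasopressors and missing y/n". It scores SOFA as normal once a patient has left the ICU for good.

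**Fluid protocol.** Appendix E has a separate footnote: "Renal failure is defined as dialysis dependence, oliguria with serum creatinine > 3mg/dl", followed by a further oliguria criterion.

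**The concern.** Dialysis lowers creatinine, so the main renal marker can look acceptable because the kidneys are being replaced. A patient whose blood pressure is held up by a drug the table does not name can likewise score 0 or 1. Neither document has a rule that overrides the table in these cases. The SAP carries a vasopressor yes/no item forward but never turns it into a score, so a programmer must guess what a yes without a listed drug means.

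The outcome carries some weight here. Protocol Section 9.1 says that the deep sedation given with blockade may lead to hypotension needing vasopressors, and only the intervention arm is protocolized to deep sedation (Sections 2 and 5.1.2). Appendix C3 exempts renal failure and vasoactive treatment of hypotension from adverse event reporting unless they are judged related to the study or of uncertain relationship. SOFA data at 48 hours also go into the safety report to the DSMB (Section 6.3.1). If supported days are scored as failure-free, a real difference in organ support would show only in part.

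**Working it through.** The plan states no figure to reproduce, so the check applies the printed scoring rule to test patients.

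**Rule (Appendix K).** Renal score = the higher of the creatinine score (below 1.2: 0; 1.2–1.9: 1; 2.0–3.4: 2; 3.5–4.9: 3; above 4.9: 4) and the urine score (below 500 ml/d: 3; below 200 ml/d: 4; otherwise, or if not recorded, no contribution). Failure means a score of 2 or more.

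**Dialysed patient, worst creatinine of the day:**

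| Creatinine (mg/dL) | Urine not recorded | 800 ml/d | 400 ml/d | 100 ml/d |
|---|---|---|---|---|
| 1.1 | 0 | 0 | 3 | 4 |
| 1.5 | 1 | 1 | 3 | 4 |
| 1.9 | 1 | 1 | 3 | 4 |
| 2.0 | 2 | 2 | 3 | 4 |

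The gap is the block of 0s and 1s: creatinine below 2.0 mg/dL, with urine output either adequate or absent from the record.

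**Circulation:**

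- Unlisted vasopressor only, MAP 60: score 1, not failure.
- Unlisted vasopressor only, MAP 72: score 0, not failure.
- Norepinephrine 0.05 µg/kg/min, MAP 72: score 3, failure.

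A patient on a listed drug as well as another agent is caught through the listed drug.

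**Where the renal gap is widest.** Through day 7, intake and output are scheduled, so oliguria can be detected if those data are used for SOFA. After day 7 no urine output is scheduled. If SOFA is collected only on the marked days, a low creatinine on day 7 is carried through days 8 to 13, and one on day 14 through days 15 to 20. Appendix B also has a footnote about collection on days 0 to 28, but its marker cannot be matched to a row in the text available. Weekly collection is therefore a condition here, not an established fact. The post-ICU rule limits all of this to patients still in the ICU or between ICU stays.

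**Size, on assumed inputs only.** Overstatement of renal-failure-free days per randomized patient = share of patients affected × misscored days each.

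| Share affected | 3 days | 7 days | 14 days |
|---|---|---|---|
| 5% | 0.15 | 0.35 | 0.70 |
| 10% | 0.30 | 0.70 | 1.40 |
| 20% | 0.60 | 1.40 | 2.80 |

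For days free of all organ failure these are upper limits, because a day with another scored failure is already not failure-free. Renal and cardiovascular misscored days may also coincide, so they should not be added.

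**Effect on a comparison.** If a share *m* of dialysis days is misscored equally in both arms, measured difference = (1 − *m*) × true difference. Suppose one arm cut dialysis from 20% to 15% of patients, at 8 days each, with no other renal failure on those days. The true gain is 0.05 × 8 = 0.40 days. With *m* = 40%, 60% or 70%, the measured gain is 0.24, 0.16 or 0.12 days. The difference shrinks but keeps its sign.

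**The case against.** The table follows a cited score, is the same in both documents, and concerns one secondary outcome. It also catches more than it may seem to. The worst value of the date counts, so a low creatinine just after dialysis is not enough, and oliguria scores 3 or 4 when urine output is used. The case report form is not among the documents, so the lack of a dialysis field is inferred from the Appendix B footnote. No rates support any estimate in days. These points stand, and they narrow the gap. They do not close it: neither document maps dialysis or another vasopressor to a score. Fidelity to the printed score is a weak defence, because the trial already records what it calls a modified SOFA (Section 6.3.2 and Appendix B).

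A reader might infer that Appendix K contradicts Appendix E. The documents do not support that. The Appendix E footnote explains when the fluid protocol withholds diuretics, whereas Section 3.9.2 sends this outcome to Appendix K. Two definitions serve two purposes. Appendix E shows only that the authors regard dialysis dependence as renal failure.

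A reader might also infer that the comparison between arms is biased by a known amount. The hypotension remark in Section 9.1 makes a difference in vasopressor use plausible, but nothing shows that dialysis, or the choice of agent, differs by arm.

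**Conclusion.** The point holds as a cheap improvement to a secondary outcome. As written, the plan credits some days on organ support as days free of that organ's failure: dialysis days with creatinine below 2.0 mg/dL throughout (or carried forward at that level) and urine output at least 500 ml/d or unrecorded, and days on only an unlisted vasopressor. Whether many or few days are affected cannot be determined from the documents. The range of 0.15 to 2.8 renal-failure-free days per patient reflects assumed rates alone. With equal misscoring in both arms the consequence is attenuation. Mortality, and the stopping boundaries that depend on it, are untouched.

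**What to change.** In Appendix K and SAP Appendix A3, state for endpoint scoring only:

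- A study day on newly started renal replacement therapy counts as a day of renal failure. Chronic dialysis present before enrolment does not.
- A study day on any vasopressor infusion of at least one hour, whatever the agent, counts as a day of cardiovascular failure.
- Both are subject to the existing requirement that the score be *new* and to the SAP's post-ICU rule.

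Add a dialysis yes/no item to the SOFA form, with chronic dialysis recorded at baseline.

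The limits in the first and third items are needed. Chronic dialysis is not an exclusion in Section 4.3, so counting every dialysis day would score long-standing dialysis as failure throughout, against the *new* requirement. It would also count dialysis after ICU discharge, which the SAP deliberately treats as normal.

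The cost is one added form item and a few sentences, since vasopressor use is already recorded. The downside is a small further departure from the printed SOFA table. Nothing in patient care changes.
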